14 DATA HANDLING AND RECORD KEEPING

14.1 DATA COLLECTION AND MANAGEMENT RESPONSIBILITIES

Data collection is the responsibility of the clinical trial staff at the site under the supervision of the site PI. The investigator is responsible for ensuring accuracy, completeness, legibility and timeliness of the data reported.

All source documents should be completed in a neat, legible manner to ensure accurate interpretation of data. When making changes or corrections, cross out the original entry with a single line, and initial and date the change. Do not erase, overwrite, or use correction fluid or tape on the original.

Research material for this study will consist of baseline patient data including demographics, co-morbidities, biochemical data, and HD treatment data (dialysate, dialysis time, target weight, UF volume, and medications) collected via patient interview and electronic medical record review. During the study HD treatments, patient vital signs (including blood pressures and weights) will be collected. Patient data will be identified with a study identification number. Patient-signed study informed consent forms will contain patient names and signatures. These consent forms will be stored separately from other study data in a locked filing cabinet in the Principal Investigator's locked office. Only the Principal Investigator and research assistant will have access to consent forms.

The collected study data will not contain participants' names, medical record numbers, social security numbers, or contact information (address, telephone number), such that these data cannot be linked back to the source patients. Data collected about patients will be labeled with a study identification number. A database linking patient names and study identification numbers will be maintained separate from the study data. This database will be password-protected and will be maintained on a password-protected UNC Department of Medicine server that is accessed via a UNC password-protected computer with anti-virus and UNC firewall protection. The study statistician (to-be-named) will have access to the de-identified electronic data.

The PI will be the primary responsible party for the oversight and management of the study data. The study research coordinator will assist with data management.

14.2 STUDY RECORDS RETENTION

Study documentation includes all case report forms, data correction forms or queries, source documents, monitoring logs/letters, and regulatory documents (e.g., protocol and amendments, IRB correspondence and approval, signed patient consent forms).

Source documents include all recordings of observations or notations of clinical activities and all reports and records necessary for the evaluation and reconstruction of the clinical research study.

Government agency regulations and directives require that all study documentation pertaining to the conduct of a clinical trial must be retained by the study investigator. In the case of a study with a drug seeking regulatory approval and marketing, these documents shall be retained for at least two years after the last approval of marketing application in an International Conference on Harmonization (ICH) region. In all other cases (as applicable to this study), study documents should be kept on file until three years after the completion and final study report of this investigational study.

14.3 PROTOCOL DEVIATIONS

According to UNC's IRB, a protocol deviation is any unplanned variance from an IRB approved protocol that:

- Is generally noted or recognized after it occurs
- Has no substantive effect on the risks to research participants
- Has no substantive effect on the scientific integrity of the research plan or the value of the data collected
- Did not result from willful or knowing misconduct on the part of the investigator(s).

An unplanned protocol variance is considered a violation if the variance meets any of the following criteria:

- Has harmed or increased the risk of harm to one or more research participants
- Has damaged the scientific integrity of the data collected for the study
- Results from willful or knowing misconduct on the part of the investigator(s)
- Demonstrates serious or continuing noncompliance with federal regulations, State laws, or University policies.

If a deviation or violation occurs please follow the guidelines below:

Protocol Deviations: UNC personnel will record the deviation in a Case Report Form and report to IRB or data and safety monitoring committee in accordance with their policies. Deviations should be summarized and reported to the IRB at the time of continuing review.

Protocol Violations: Violations should be reported by UNC personnel within one (1) week of the investigator becoming aware of the event using the same IRB online mechanism used to report Unanticipated Problems.

Unanticipated Problems: Any events that meet the criteria for "Unanticipated Problems" as defined by UNC's IRB must be reported by the Study Coordinator using the IRB's web-based reporting system.

14.4 PUBLICATION AND DATA SHARING POLICY

This study will comply with NIH Public Access Policy, which ensures that the public has access to the published results of NIH funded research. It requires scientists to submit final peer-reviewed journal manuscripts to the digital archive PubMed Central upon acceptance for publication. The study will be registered at clinicaltrials.gov, sponsored by the National Library of Medicine.

16 CONFLICT OF INTEREST POLICY

The independence of this study from any actual or perceived influence, such as by the pharmaceutical industry, is critical. Therefore, any actual conflict of interest of persons who have a role in the design, conduct, analysis, publication, or any aspect of this trial will be disclosed and managed. Furthermore, persons who have a perceived conflict of interest will be required to have such conflicts managed in a way that is appropriate to their participation in the trial. All study personnel will adhere to the the conflict of interest policy set forth by the University of North Carolina at Chapel Hill.

Appendix A: Transthoracic Echocardiography (TTE) Protocol

The imaging protocol described below is designed primarily to assess intradialytic left ventricular systolic function by measuring myocardial strain by speckle tracking imaging. Left ventricular ejection fraction by two-dimensional echocardiography, right ventricular function, and left ventricular diastolic function will also be evaluated.

Image acquisition

Data storage and labeling

- Studies should be labeled with the participant's identification number, study number, and date of the study.
- Each echocardiographic study will be stored on the hard drive of the ultrasound machine and copied in native and DICOM formats onto a compact disc for subsequent off-line analysis.

General procedure

- Imaging will be performed during quiet respiration with the subject in the left lateral decubitus position. All tracings will be recorded with a simultaneous electrocardiogram.
- Harmonic imaging will be utilized, and transducer orientation and gain settings will be carefully adjusted to optimize imaging of the epicardial and endocardial surfaces of the ventricles.
- Tissue Doppler imaging will be performed at a 25 mm/second sweep speed.\
- 2D images will be stored digitally in loops consisting of 3 beats. Tissue Doppler tracings containing 3 consecutive frames will be stored for each spectral display.

Imaging protocol

As described in detail below, images should be recorded in the following sequence:

Apical 4-chamber view

Apical 2-chamber view

Apical long axis view

Apical 4-chamber view: A standard apical 4-chamber view of the heart will be obtained with the ultrasound beam oriented to obtain the maximal dimensions of the left and right ventricles. Tissue Doppler imaging of mitral and tricuspid annular motion will then be performed. Initially the lateral mitral annulus will be interrogated, placing the sample volume within the lateral wall of the left ventricle, adjacent to the mitral annulus. The transducer will be oriented so that the ventricular wall is parallel to the cursor, and 5 consecutive beats showing peak Sm, Em, and Am velocities will be recorded. The septal mitral annulus will be interrogated in similar fashion. The anterior tricuspid annulus will then be interrogated by placing the sample volume within the right ventricular free wall, adjacent to the tricuspid annulus.

Apical 2-chamber view: Standard 2-chamber images of the left ventricle, with the transducer angled to maximize the left ventricular long axis dimension, will be acquired.

Apical long axis view: Standard apical long axis images of the left ventricle, with the transducer angled to maximize the left ventricular long axis dimension, will be acquired.

Image analysis

Global longitudinal strain: Left ventricular function will be quantified by 2-dimensional speckle tracking echocardiography-derived global longitudinal strain. The apical 4-chamber, 2-chamber, and long axis views will be optimized and analysed offline using a dedicated computer workstation equipped with Philips QLab software. Aortic valve closure time will be defined on the apical long-axis view. After the mitral annulus and apical left ventricular endocardium are identified, a region of interest will be automatically defined and edited as necessary. Global longitudinal strain will be calculated as the average of all 3 apical views.

Left ventricular ejection fraction: The areas of the left ventricle at end-diastole and at end-systole will be quantified by tracing the endocardial border (excluding trabeculations and papillary muscles) in the apical 2-chamber and 4-chamber views. Left ventricular volumes at end-diastole and at end-systole will be computed using the biapical Simpson's rule. Ejection fraction will be calculated as percentage change in left ventricular volumes.

Early diastolic myocardial velocity (E_m): Left ventricular diastolic function will be quantified as the early diastolic myocardial velocity (E_m) calculated as the average of early diastolic velocities recorded at the medial and lateral mitral annulus.

Tricuspid annulus systolic excursion velocity (S_t): Right ventricular systolic function will be quantified as the peak systolic excursion velocity (S_t) of the anterior tricuspid annulus.

Appendix B: Symptom Monitoring Questionnaire

PATIENT-REPORTED SYMPTOMS DURING DIALYSIS

INSTRUCTIONS

Please respond to each statement by marking one box per row.

We are interested in the symptoms you had DURING your dialysis treatments LAST WEEK. Respond ONLY based on the dialysis treatments last week.

During your dialysis treatments last week, did you have CRAMPING?
	No cramping 	Mild cramping 	Moderate cramping 	Severe cramping 	Very severe cramping 
--	---	---	---	---	--

During your dialysis treatments last week, did you have NAUSEA or UPSET STOMACH?
	No nausea 	Mild nausea 	Moderate nausea 	Severe nausea 	Very severe nausea 
---	---------------------------------------	---	---	---	--

During your dialysis treatments last week, did you have VOMITING or THROWING UP?
	No vomiting 	Mild vomiting 	Moderate vomiting 	Severe vomiting 	Very severe vomiting 
---	---	---	---	---	--

During your dialysis treatments last week, did you have
 
DIZZINESS or LIGHTHEADEDNESS?
	No dizziness 	Mild dizziness 	Moderate dizziness 	Severe dizziness 	Very severe dizziness 
---	--	--	--	--	---

During your dialysis treatments last week, did you have
 
RACING HEART or HEART PALPITATIONS?
	No racing heart 	Mild racing heart 	Moderate racing heart 	Severe racing heart 	Very severe racing heart 
---	---	---	---	---	--

During your dialysis treatments last week, did you have
 
CHEST PAIN?
	No chest pain 	Mild chest pain 	Moderate chest pain 	Severe chest pain 	Very severe chest pain 
---	---	---	---	---	--


During your dialysis treatments last week, did you have
 
SHORTNESS OF BREATH?
	No shortness of breath 	Mild shortness of breath 	Moderate shortness of breath 	Severe shortness of breath 	Very severe shortness of breath 
--	--	--	--	--	---

During your dialysis treatments last week , did you have THIRST or DRY MOUTH?	No thirst 	Mild thirst 	Moderate thirst 	Severe thirst 	Very severe thirst 
--	---------------------------------------	---	---	---	--

During your dialysis treatments last week , did you have HEADACHE?	No headache 	Mild headache 	Moderate headache 	Severe headache 	Very severe headache 
---	---	---	---	---	--

During your dialysis treatments last week , did you have ITCHING?	No itching 	Mild itching 	Moderate itching 	Severe itching 	Very severe itching 
--	--	--	--	--	---

During your dialysis treatments last week , did you have RESTLESS LEGS or DIFFICULTY KEEPING LEGS STILL?	No restless legs 	Mild restless legs 	Moderate restless legs 	Severe restless legs 	Very severe restless legs 
---	--	--	--	--	---

During your dialysis treatments last week , did you have TINGLING or FEELING OF PINS AND NEEDLES?	No tingling 	Mild tingling 	Moderate tingling 	Severe tingling 	Very severe tingling 
--	---	---	---	---	--

During your dialysis treatments last week, did you have OTHER SYMPTOMS? (write-in) <hr/> <hr/> 
	No	Mild	Moderate	Severe	Very severe
					

AFTER your dialysis treatments LAST WEEK, how long did it take for you to recover?
	<hr/> 
_____ hour(s)

---	----------------------------

Ultrafiltration (UF) profiling and outcomes among individuals on maintenance hemodialysis: statistical analysis plan

Primary Analysis

Depending on the type of various endpoints, we propose to perform the following tests to test the difference between UF profile and conventional treatment.

- **Binary Outcomes**
 - We will perform repeated measure logistic regression by regressing the binary outcome on the treatment indicator and test if the coefficient before the treatment indicator is significant. Each subject will have a random intercept. The model is given by
$$\text{logit}(\text{outcome}) \sim 1 + \text{treatment} + (1|ID)$$
- **Continuous Outcomes**
 - We will perform repeated measure linear regression by regressing the continuous outcome (percentage outcome will be log-transformed) on the treatment indicator and test if the coefficient before the treatment indicator is significant. Each subject will have a random intercept. The model is given by
$$\text{outcome} \sim 1 + \text{treatment} + (1|ID)$$
- **Categorical Outcomes**
 - We will perform repeated measure multinomial regression by regressing the categorical outcome on the treatment indicator and test if the coefficient before the treatment indicator is significant. Each subject will have a random intercept. The model is given by
$$\text{multi-logit}(\text{outcome}) \sim 1 + \text{treatment} + (1|ID)$$

Quality Check

For patients who dropped out during the study, normalize endpoints to the same scale as the other patients, depending on the type of endpoints.

Sensitivity Analyses

1. Exclude participants who dropped out from all analyses.
2. Exclude participants who had endpoint data drawn "off-schedule" (troponin T, symptoms, etc.) from individual endpoint analyses.
3. Exclude participants who had an abnormality with their troponin T blood draw from troponin T-related analyses.
4. Test for difference by order of randomization (UF profiling --> conventional --> UF profiling --> conventional) vs. (conventional --> UF profiling --> conventional --> UF profiling)
5. Test for difference by clinic (site 1 vs. site 2)

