4.2.2 SECONDARY ENDPOINTS

- 1) Systolic BP change: measured on a per-treatment basis; defined as pre-HD – nadir intra-HD systolic BP (mmHg)
- 2) Nadir systolic BP: measured on a per-treatment basis; defined as the minimum intradialytic systolic BP (mmHg)
- 3) Target weight achievement: measured on a per-treatment basis: defined as post-HD weight within 1 kg of prescribed target weight.
- 4) Weight difference: measured on a per-treatment basis; defined as target weight – post-HD weight (kg)
- 5) Patient acceptance: measured after treatment 9 of each phase; response to the following question, "If recommended by your physician, would you be willing to adopt the HD prescription you have received during the last 9 treatments?"

6) TTE ejection fraction (EF): measured 30 minutes before HD end during 7th treatment in the first phase of each treatment type (once during conventional and once during UF profiled treatment); defined as % EF change (baseline – intradialytic EF), see Appendix A for TTE protocol

7) Patient-reported symptoms: measured after the 1st HD treatment each week; see Appendix B for data collection form.

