5.2 PARTICIPANT EXCLUSION CRITERIA

Patients meeting any of the following exclusion criteria will not be eligible for randomization.

- Systolic BP unable to be measured by arm cuff
- >1 hospitalization during 4-week screening period
- Unstable angina per treating nephrologist

- End-stage cirrhosis per treating nephrologist
- New York Heart Association class IV heart failure per treating nephrologist
- Pregnant
- Dialysis treatment schedule increases to more than 4 times per week
- Incarcerated
- Anticipated kidney transplant within 6 months per treating nephrologist
- Non-adherence to HD prescription (>2 unexplained absences during 4-week screening period)
- Sodium profiling or UF profiling in standing HD prescription
- Decisionally challenged, unable to provide informed consent

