5.3 STRATEGIES FOR RECRUITMENT AND RETENTION

The recruitment goal is 36 participants (to account for drop-out) with study completion goal of 30 participants. The PI, a nephrologist, will identify eligible subjects from participating dialysis clinic (Carolina Dialysis Carrboro, Siler City) patient rosters and offer opportunity to participate in the study. If the patient does desire to participate in the research study, informed consent will be obtained by the PI or research staff. A study information sheet will be made available in the clinic for patients who desire additional information about the study. Participants will receive \$20 for their time spent participating in the baseline TTE procedure because it is the only TTE performed outside of participants' regular dialysis treatment time. Participants will be compensated \$45 for each 9 week treatment period and \$20 for the baseline period TTE (\$200 for full study completion).

Participants may miss study treatments. Missed study treatments will be considered "missed" and will not be made-up. For example, if a patient misses treatment #9 from arm 1, the patient will start wash-out treatments at the next treatment and will have missing data for treatment #9. The permeated design of the study arms (alternating conventional, UF profile, conventional, UF profile) was selected to maximize opportunities for data collection under each treatment paradigm. If participants are lost to follow-up (death, withdrawn consent, move to a new dialysis center), additional participants will be recruited until a study size of 30 participants is reached.

Based on the composition of the patient populations at the participating UNC sites, the expected sex breakdown is 50% male and 50% female and the expected enrollment of Hispanic or Latino participants is 10%. No exclusion by sex or by ethnic/ racial background will be made. There are no expected differences in the response to UF profiling across sex or racial/ ethnic groups. Children (individuals < 18 years) and vulnerable participants are not included in the study.

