6.1.2 DURATION OF THERAPY

Patients will undergo 9 treatments during each phase for a total of 18 conventional HD treatments and 18 UF profiled treatments. Patients will undergo 3 wash-out HD treatments between phases. There will be a total of 45 study treatments (36 study treatments and 9 washout treatments). The baseline study visit will involve a history and physical and baseline transthoracic echocardiography study. The entire study duration for each individual is 16 weeks (15 treatments and 1 baseline study visit).

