7 STUDY PROCEDURES AND SCHEDULE

7.1 STUDY PROCEDURES/EVALUATIONS

7.1.1 STUDY SPECIFIC PROCEDURES

UF profiled HD treatments (intervention): The study treatments will be administered at routine, scheduled outpatient thrice-weekly HD clinic visits. Dialysis clinic nursing staff will select UF profile 2 on the dialysis machine at the start of each UF profiled treatment. Clinic nursing staff have experience using UF profiling as it is a standard HD machine setting. Dialysate composition and HD medications will be per baseline prescription determined by the treating nephrologist. Total UF volume and target weight will be determined by the treating nephrologist.

Medical history: At baseline, the participant’s medical history will be taken from the electronic medical record and confirmed verbally with the patient. The medical history will include a review of co-morbid conditions, medications

and performance of a physical examination (Vital signs- BP, heart rate, respiratory rate, weight, height; systems- cardiovascular, pulmonary, neurological)

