7.2.2 OTHER ASSAYS OR PROCEDURES

TTE: Patients will undergo intradialytic TTE at baseline (within 6 weeks prior to study start) and 30 minutes prior to HD end ("peak stress") during treatment 7 of the first phase of each treatment type (once during conventional and once during UF profiled treatment) (1 TTE during UF profiled HD and 1 during control HD). Study TTEs will be performed by a trained sonographer with a Philips CX50 ultrasound system (Philips North America).

Blood volume monitoring: Blood volume monitoring will be performed continuously throughout each study treatment via a Crit-line™ (standard-of-care non-invasive relative blood volume monitoring tool used as part of standard dialysis treatments).

Plasma refill test: Using the blood volume monitor, a plasma refill test will be performed 10 minutes before HD end during the 7th treatment of each phase. At the start of the treatment, UF time will be set 10 minutes less than treatment time. When the dialysis UF ends, study staff will document the hematocrit (%) from the blood volume monitor, and when the treatment ends, document the blood volume monitor hematocrit (%) again. Plasma refill tests are part of the blood volume monitoring protocols at the selected units and are familiar to staff.

Patient acceptance: At the end of the 9th study treatment of each phase, study staff will ask the participant the following question: "If recommended by your physician, would you be willing to adopt the HD prescription you have received during the last 9 treatments?"

Symptom assessment: At the conclusion of the 1st study treatment each week, study staff will ask patients to complete a symptom questionnaire (Appendix B).

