7.3.7 SCHEDULE OF EVENTS TABLE

Procedures	Baseline (6 week prior to study start)	Every study HD treatment	Before and after 7 th HD treatment of each phase	During 7 th HD treatment of each phase (twice per treatment type)	During 7 th HD treatment in the first phase of each treatment type (once per treatment type)	After 9 th HD treatment of each phase	After 1st HD treatment of each week (3x/phase)
Baseline laboratory testing	X						
Baseline history and physical	X						
Pregnancy status inquiry	X						
BP monitoring	X	X					
Weight monitoring	X	X					
Blood volume monitoring	X					X	
Troponin T laboratory testing			X				
TTE	X				X		
Plasma refill test	X			X			
Patient acceptance assessment						X	
Symptoms assessment						X	

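### The weekly symptom form looks back past the start of each phase, leaves the last one to three treatments of at least phase 4 unrecalled, and has no rule assigning it to a treatment

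*Combined protocol and SAP*

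**What the plan says.** The recall window is in the Appendix B instructions: "We are interested in the symptoms you had DURING your dialysis treatments LAST WEEK. Respond ONLY based on the dialysis treatments last week". The recovery-time item at the end of the form has the same window.

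The timing appears in three places in the protocol:
- Section 4.2.2: "Patient-reported symptoms: measured after the 1st HD treatment each week; see Appendix B for data collection form".
- Section 7.2.2: "At the conclusion of the 1st study treatment each week, study staff will ask patients to complete a symptom questionnaire (Appendix B".
- The column header in the Section 7.3.7 table: "After 1st HD treatment of each week (3x/phase". I rely on this header and on the two sections above, not on where the mark in the symptom row falls, because table columns may have shifted in the extracted text.

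On the calendar, Section 7.1.1 says "The study treatments will be administered at routine, scheduled outpatient thrice-weekly HD clinic visits". Each phase has nine treatments, with three wash-out treatments between phases (Sections 4.1 and 6.1.2), and Section 6.1.2 adds: "There will be a total of 45 study treatments (36 study treatments and 9 washout treatments". Missed treatments are not made up. Section 5.3 gives the example that "if a patient misses treatment #9 from arm 1, the patient will start wash-out treatments at the next treatment".

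On analysis, Section 10.4.3 compares symptom occurrence between treatments by GEE. The SAP regresses each outcome on a treatment indicator with a random intercept per participant. Neither says whether a form takes the treatment of the week in which it was completed or of the week it recalls. Neither says what happens to a form about wash-out or pre-study sessions.

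**The concern.** A form completed at the start of a week about the week before is always one week behind. The first form completed in a phase therefore describes, wholly or partly, dialysis given before that phase. The last treatments of a phase are described only if someone collects a form after the phase has ended.

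The documents leave two things open. The first is collection: three forms per phase can mean three completed during the phase or three about the phase. The second is labelling: two analysts could code the same form differently and both comply with the SAP. What is at stake is how much of each phase the symptom endpoint covers and, on one possible coding, whether some forms labelled as UF profiling describe non-profiled sessions. Patient-reported outcomes are part of the stated objective in Section 3.

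**Working it through.** **Inputs.** Nine treatments per phase, four phases, three wash-outs of three sessions (Sections 4.1, 6.1.2); three sessions per week (Section 7.1.1); a form at the first session of each week recalling the previous week's three sessions (Sections 4.2.2, 7.2.2, Appendix B). The documents do not fix the weekday on which phase 1 begins, so all three positions are shown.

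**The plan's own figures.** 4 × 9 = 36 and 3 × 3 = 9, giving 45 sessions. 9 / 3 = 3 forms per phase, as the schedule states.

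**What the forms recall.** One phase plus one wash-out is 9 + 3 = 12 sessions, or 12 / 3 = 4 whole weeks, so the pattern repeats in phases 2 to 4.

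| Treatment 1 is the week's | Forms after treatments | Outside sessions on first form | Own-phase sessions recalled within phase | Never recalled within phase |
|---|---|---|---|---|
| 1st session | 1, 4, 7 | 3 | 0 + 3 + 3 = 6 of 9 | 7, 8, 9 |
| 2nd session | 3, 6, 9 | 1 | 2 + 3 + 3 = 8 of 9 | 9 |
| 3rd session | 2, 5, 8 | 2 | 1 + 3 + 3 = 7 of 9 | 8, 9 |

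**Coverage of the 36 study treatments** (start on 1st / 2nd / 3rd session):
- Within phases only, 12 forms: 4 × 6 / 4 × 8 / 4 × 7 = 24 / 32 / 28.
- Plus one form in each of three wash-outs, 15 forms: 24 + 9 / 32 + 3 / 28 + 6 = 33 / 35 / 34. Only the end of phase 4 is missing.
- Plus one form after phase 4, 16 forms: 33 + 3 / 35 + 1 / 34 + 2 = 36 / 36 / 36.

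With a start on the first session, four of those 16 forms recall only outside sessions. The other 12 cover all 36 treatments in whole-phase weeks. With a mid-week start, each phase has two whole-phase weeks and two mixed weeks, so 8 of the 16 forms are mixed.

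**Labelling.** If a form takes the treatment of the week it recalls, a whole-phase week is not diluted. Suppose instead that it takes the treatment of the phase in which it was completed, that wash-out is non-profiled, and that there is no carry-over. Conventional-labelled forms then describe no profiled sessions, and UF-labelled forms describe profiled sessions in the shares above. The contrast on the difference scale becomes 6/9, 8/9 or 7/9 of its true size: 0.67 / 0.89 / 0.78. Shares are counted by session, so for mixed weeks these are approximate for a yes/no weekly symptom. The SAP's log-odds coefficient would shrink by a different amount.

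That wash-out is non-profiled is an inference. Section 5.2 excludes patients with "Sodium profiling or UF profiling in standing HD prescription", and Section 7.5 allows no change to usual dialysis other than profiling in the profiled arms.

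**The case against.** The strongest reply is that a weekly-recall form given at the first session of the next week is coherent, and that all that is missing is one line of coding. The form asks about symptoms during last week's sessions and the analysis compares treatments, so the natural reading puts a symptom with the session in which it occurred. This largely stands. It is why the form's wording should stay, and why the 0.67 to 0.89 factors are conditional.

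A second reply is that coverage loss is small. Forms are due every week, and wash-out sessions are counted among the 45, so 33 to 35 of 36 treatments may be covered. That is a fair reading, but the phrase three per phase equally supports collection within phases only, at 24 to 32. On both readings the end of phase 4 is lost.

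Third, the mid-week rows are less secure than the first row. Section 7.2.2 refers to the first study treatment of the week. With a mid-week start, that would add a form after treatment 1 of phase 1, which does not fit three per phase. That form would recall only pre-study sessions, so coverage would not change. The same alignment in phases 2 to 4 also assumes that missed wash-out sessions are not made up, whereas the Section 5.3 example concerns a missed study treatment. Finally, if patients answered for the past seven days including the current session, the outside sessions on the first form would number 2 / 0 / 1 rather than 3 / 1 / 2. The previous calendar week is the plainer reading.

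A reader might infer that the planned symptom comparison is biased towards no difference, or that forms mix the two arms. The documents do not support the first, because no text labels forms by phase of completion. The second is wrong: the three-session wash-out means that no form recalls both arms.

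**Conclusion.** The mismatch and the missing rule are real. Taking last week as the previous calendar week and three sessions per week, the first form in each phase recalls one to three sessions outside it. The final one to three treatments go unrecalled in every phase (within-phase collection) or in phase 4 only (wash-out weeks included). With labelling by recalled week, that loss of coverage is the whole cost. Dilution needs three further conditions: labelling by phase of completion, non-profiled wash-out, and no carry-over.

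This concerns one of seven secondary endpoints in a pilot, with no power figure stated for symptoms. No primary endpoint uses the form. Importance is minor to moderate. Confidence is high in the arithmetic and in the absence of a rule, but not in any particular effect on results.

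**What to change.** Keep the last-week wording and make two changes.

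**Schedule.** Collect the form at the first session of the week after each study week, including the first wash-out week and the first routine week after phase 4. If the count of study treatments starts on a week's first session, forms fall after treatments 4 and 7 and at the first session after the phase. That gives 4 × 3 = 12 forms, all about whole-phase weeks, and no dialysis session has to move. A mid-week start needs 16 forms, 8 of them about mixed weeks.

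**SAP.** State that:
- each form takes the treatment of the week it recalls;
- forms recalling only wash-out or pre-study sessions are not phase data;
- mixed weeks are left out of the main analysis and added in a sensitivity analysis;
- the post-phase form counts as on schedule for sensitivity analysis 2, which does not define off-schedule for symptoms.

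Forms already collected can be re-assigned to the recalled week from their completion dates.

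**Cost.** One form at a routine visit after phase 4, outside the 45 scheduled sessions; a small amendment needing IRB approval under Section 13.2; and, with mid-week starts, the mixed-week forms dropped from the main analysis. The coding rule alone would remove any dilution in whole-phase weeks, but would not recover the lost coverage.
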